We will use a prospective design, in which patients scheduled for elective CABG will be recruited and evaluated prior to CABG (Pre-surgery) and upon discharge (Discharge) for physical function (SPPB Testing and 6 min walk). Patients will be recruited for this study during the normal process of clinical recruitment for cardiac rehabilitation. This includes patients from cardiothoracic consultation lists and/or those scheduled for elective CABG. In some instances, we will identify patients from cardiothoracic consultation lists who are or will be scheduled for CABG, but are not on the surgical unit. We will contact these patients by phone regarding participation in cardiac rehabilitation and, at that time, introduce this research study. Patients will be randomized (1:1) to NMES or control intervention (n=18/group; Treatment Phase), with stratification for age and sex. Following completion of the 4 wk intervention,

volunteers will undergo Post- Testing, which will be identical to Pre-surgery and Discharge testing. Each protocol phase is described below.

Pre-surgery testing Baseline testing will occur prior to CABG surgery and at discharge and consist of functional assessment by the SPPB and a quality of life (QOL) questionnaire (MOS-SF36). Tests are described below.

Discharge testing will repeat Pre-surgery testing and include a 6MW. At this time, volunteers will receive an accelerometer, which will be worn during three (3) 5-day periods during the Treatment phase.

Treatment Phase

Patients will be randomized (1:1) to NMES or control intervention and will continue in this Treatment phase until 4 weeks post-CABG surgery.

4 wk Post-surgery testing will be identical to Discharge testing.

Procedures:

All of the procedures and interventions on volunteers recruited for these studies are carried out solely for research purposes, as none are part of standard therapy in CABG patients.

Physiological Testing (during Pre-surgery (excluding 6 MW), Discharge and 4 wk Post-surgery testing)

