NMES will be carried out bilaterally on the quadriceps using a portable stimulator (EMPI Continuum). Two adhesive electrodes will be affixed to the anterior surface of each thigh: ~1 cm distal to the inguinal crease and ~5 cm proximal to the patella, just lateral to the midline of the thigh to assure that it does not interfere with incisions for vein harvest. Symmetrical, biphasic pulses (400 μ s duration at 25 Hz) will be used, with a duty cycle of 25% (10 s on, 30 s off). Patients will be trained to conduct NMES sessions and will select stimulation intensities sufficient to cause visible muscle contractions below their pain threshold. Training in the use of the NMES device will begin within 96 hrs of transfer to the surgical step down unit. This training will consist of one session per day of ~15 min to familiarize the volunteer with the unit and the exercise/contraction stimulus. Upon discharge, NMES sessions will occur 5 d/wk once per day for 45 min per occasion (5 min low-intensity warm-up, 40 min higher-intensity stimulation) for 4 wks. This program is meant to mimic an aerobic-type exercise stimulus (8) and has been shown in heart failure patients to have functional benefits over a similar treatment period (9, 10). The 4 wk duration reflects the approximate average time that most CABG patients take to enter CR at our center. We acknowledge that the NMES training load is substantial, but have modeled this program on others that have shown morphological and functional effects in heart failure patients (11). At this exploratory stage, we feel that it is essential to use a stimulus that affects muscle size and function, with future studies modifying the NMES dose to establish a threshold that elicits a training effect with the highest subject

compliance rate. Daily logs and weekly phone contacts will be used to track compliance, and compliance will be covertly monitored using the device software.

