Adverse events will be reported by one of 3 mechanisms. First, the joint University of Vermont/University of Vermont Medical Center (UVMMC) Committee for Human Subject Research Adverse Event Reporting Document. These reports will be sent to the office of the Committee for Human Research in the Medical Science (CHRMS) within 2 days of the event. Reporting any adverse events will be the responsibility of the PIs. The CHRMS will make a determination as to whether additional reporting requirements are indicated. Additionally, the UVMMC Patient Safety Reporting system (SAFE), which may be initiated by health care center staff or study personnel. These forms will be forwarded within 3 days to the PI, UVMMC Risk Management Office, CHRMS and other appropriate agencies, as indicated by the nature of the report. Reviews of protocol specific adverse events will be

performed no less than annually. Additionally, any adverse event that occurs will be forwarded to the PIs for reporting to the Human Subject Research Protection Office within 1 week of occurrence. Of note, these protections against risk include both physical risks to the volunteers, as well as risks associated with any breach in confidentiality.

On an annual basis, Drs. [name] and [name] will assess data being gathered and safety of volunteers to assess the pattern or frequency of events to identify occurrence of any event or problem that alters the safety profile of the procedures being performed. The exception would be occurrence of a serious adverse event or unanticipated problem that necessitates re-evaluation of the expected risk of the study procedures at an earlier time point. Additionally, they will evaluate data collection and storage to ensure the confidentiality of data and quality. Each of these evaluations will be followed by reports of study progress and patient safety to the University of Vermont CHRMS via yearly progress reports.

Withdrawal Procedures:

Volunteers will be withdrawn if the research team, clinician and/or safety officer feels that further participation in the study or performance of any procedure associated with this study would, in any way, put the volunteer at undue risk or not be in their best interest. Moreover, volunteers may be withdrawn if s/he fails to attend scheduled visits or do not comply with instructions from research staff.

Sources of Materials:

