An individual research record will be kept on each volunteer in compliance with HIPAA standards. This record will contain identifying data, demographic information and results from all clinical research measurements and evaluations. The results of all testing will be kept confidential. All materials gathered in conjunction with the proposed studies will be used for research purposes only and will be available only to research personnel working on these studies, who have obtained proper training in human subjects research and privacy protection.

Statistical Analysis Plan:

Our primary goal is to assess changes in SPPB score and 6 MW between study groups to test whether NMES prevents the erosion of functionality from admission to 4 wk post-discharge (approximate time for starting CR). A general linear mixed model will be used, with group and time as fixed effects. The primary comparison will be between measures at admission and 4 wks post-discharge, as changes over this time period will reflect the effects of the surgery, post-op recovery and post-discharge/pre-CR periods. Because function may be impaired pre-surgery due to angina/dyspnea/etc, post-surgery measures may be a better indicator of functional capacity and we have the ability to calculate the changes in these measures from Discharge to 4 wks post-surgery. We will assess QOL by questionnaire and activity by accelerometry as secondary outcomes to determine if NMES improves patient-reported QOL and free-living daily activity, respectively, vs. usual care. Covariates (eg, length of stay, time to start of CR, admission SPPB, etc) can be included in the models to control for potential confounders that might differ by group in the event that randomization fails to equate groups for these variables.

DRUG AND DEVICE INFORMATION

Drug (s) **Not applicable**

Device (s) **Not applicable**

The interventional device used in this study: EMPI Continuum complete electrotherapy system has received FDA approval (501K: K093324) for retarding disuse-related atrophy, which we believe is one of the primary mechanisms whereby CABG patients become more functional disabled in the early, post-surgical period. That is, muscle disuse secondary to pain, limited range of motion and muscle weakness causes skeletal muscle fiber atrophy and weakness, as well as mitochondrial rarefaction and dysfunction that further impair physical fitness.

Is it FDA approved:

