SUBJECT CHARACTERISTICS, IDENTIFICATION AND RECRUITMENT

Prior to our rationale for subject selection, we provide a brief accounting of inclusion/exclusion criteria. Ambulatory patients (50-80 yrs of age) scheduled for elective CABG and able to give informed consent will be recruited. Patients will be excluded if they have: 1) rheumatoid arthritis or other inflammatory/autoimmune diseases; 2) cancer, excluding non-melanoma skin cancer; 3) exercise-limiting peripheral vascular disease, neuromuscular disease or lower extremity neuromuscular dysfunction related to prior cerebrovascular event; 4) body mass index ≥ 38 kg/m² or 5) significant (moderate or greater) valvular heart disease that was not corrected surgically. We will also exclude patients with an existing lower blood clot or an implanted pacemaker or ICD, as both are contraindications for NMES (1). Patients will be excluded from further study post-operatively if they have serious complications that prolong hospitalization beyond 7 d post-surgery (eg, stroke, prolonged intubation, infection, etc), although this will likely be a small proportion of the population.

These criteria were chosen to obtain a cohort of CABG patients who are free of other clinical conditions that may complicate our ability to detect an effect of NMES on physical function (eg, cancer w/ its accompanying treatments or motor deficits due to CVA, etc) and who may have difficulty conducting the NMES (eg, very obese individuals may have difficulty obtaining muscle contractions with the NMES device because fat in their legs serves as an electrical insulator). Finally, we exclude those volunteers with contraindications for NMES use.

Literature cited:

1. Houghton, P. E., Nussbaum, E. L., and Hoens, A. M. (2010) Electophysical agents. Contraindications and precautions: an evidence-based approach to clinical decision making in physical therapy. *Physiother Can* **62**, 1-80

Number of Subjects:

We intend to enroll 48 volunteers. This will allow for n=36 to complete the study, conservatively assuming 25% total attrition rate: 15% dropout, 10% non-compliance, based on prior studies of NMES use in post-surgical populations (1) and compliance data in our prior training studies (85-95% compliance).

Literature cited:

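### Non-compliance is counted as attrition and allowed as a reason for withdrawal, and no rule keeps non-compliers in the 4-week test or analyses them as randomised

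*Combined protocol and SAP*

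**What the plan says.** Number of Subjects sets enrolment at 48 and explains: "This will allow for n=36 to complete the study, conservatively assuming 25% total attrition rate: 15% dropout, 10% non-compliance". Dropout and non-compliance are separate items, and both are subtracted. Study Design gives the resulting group size: "Patients will be randomized (1:1) to NMES or control intervention (n=18/group; Treatment Phase". Withdrawal Procedures adds that "volunteers may be withdrawn if s/he fails to attend scheduled visits or do not comply with instructions from research staff".

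On the final assessment, Study Design says that once the 4-week intervention is finished "volunteers will undergo Post- Testing, which will be identical to Pre-surgery and Discharge testing". It does not say what happens to someone who stopped the device or used it little. The NMES description under Treatment phase tracks use by logs, weekly calls and device software, but gives no threshold for non-compliance. It also concedes: "We acknowledge that the NMES training load is substantial" (45 min, 5 days a week, 4 weeks). Controls get no device. They do have weekly contact and test visits, and at discharge "volunteers will receive an accelerometer, which will be worn during three (3) 5-day periods during the Treatment phase".

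The Statistical Analysis Plan says: "A general linear mixed model will be used, with group and time as fixed effects". It adds: "Covariates (eg, length of stay, time to start of CR, admission SPPB, etc) can be included in the models" if the groups turn out unbalanced. It names no analysis set, does not state that participants are analysed as randomised, and has no rule for follow-up after withdrawal or for missing 4-week values.

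**The concern.** Someone who has not dropped out but has used the device little can still be measured. The sample size nevertheless treats that person as lost, and the withdrawal rule lets staff make the loss real. Compliance is judged after allocation and without a threshold, so who is lost depends on decisions that randomisation does not protect.

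Non-compliance with NMES sessions can arise only in the NMES arm, so uneven loss is plausible. Controls can also fail to comply with their own tasks, so the actual split is unknown. If the losses are uneven, and those lost would have changed differently from those kept, the group comparison is biased even when NMES does nothing.

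The direction cannot be known in advance:

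- If non-compliers are recovering badly, the bias favours NMES.
- If they stop because they feel well, it works against NMES.
- If they stop for discomfort unrelated to recovery (Risks/Benefits mentions painful contractions), it is close to zero.

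**Working it through.** **The plan's own figures.** 48 × (1 − 0.25) = 36 and 36 / 2 = 18, which agrees with the group size in Study Design. The 25% is 48 × 0.15 = 7.2 dropouts plus 48 × 0.10 = 4.8 non-compliers. The arithmetic is correct, and it shows that the 36 excludes non-compliers. With only dropout removed, 48 × 0.85 = 40.8, or 20.4 per arm.

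**Assumptions not in the documents.** 24 are randomised per arm and 20.4 remain after dropout. There is no treatment effect. Would-be non-compliers are equally common in both arms, and their SPPB change is worse by a gap D of 0.5 to 1.0 SD. Dropout is unrelated to outcome. The split of the 4.8 losses between arms is varied.

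**Bias formula.** If NMES loses all its non-compliers, its retained mean is that of compliers. Control still holds a share s of would-be non-compliers, so its mean is lower by s × D. The bias towards NMES is therefore s × D.

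- Even split (2.4 and 2.4): both arms retain compliers only, so s = 0 and the bias is 0.
- 75/25 split (3.6 and 1.2): control keeps 3.6 − 1.2 = 2.4 of 20.4 − 1.2 = 19.2, so s = 0.125. The bias is 0.06 to 0.13 SD.
- All 4.8 in NMES: s = 4.8 / 20.4 = 0.235. The bias is 0.12 to 0.24 SD.

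**Simulation.** 100,000 runs, 20 per arm, unit-SD change, two-sided 5% t-test. The nominal false-positive rate favouring NMES is 2.5%.

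| Losses | D = 0.5: bias (SD); false positives for NMES | D = 1.0: bias (SD); false positives for NMES |
|---|---|---|
| Everyone kept | 0.00; about 2.5% | 0.00; about 2.5% |
| Even split | 0.00; about 2.5% | 0.00; about 2.5% |
| 75/25 | 0.063; 3.8% | 0.126; 5.2% |
| NMES only, 10% of arm | 0.049; 3.5% | 0.101; 4.6% |
| NMES only, 20% of arm | 0.099; 4.6% | 0.200; 7.7% |
| NMES only, 23.5% of arm | 0.120; 5.2% | 0.236; 8.9% |

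With the gap reversed (non-compliers better), the 75/25 bias is −0.064 and −0.124 SD. At the larger gap, false positives against NMES are 5.1%.

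**Does the mixed model repair this?** 8,000 runs, three visits, correlation 0.5 or 0.8, maximum likelihood, 4-week value missing for those removed, 75/25 split:

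- Gap arises after discharge: bias 0.060 to 0.120 SD.
- Half the gap is already visible at discharge: 0.046 to 0.098 SD.
- All of it is visible at discharge: 0.039 to 0.081 SD.

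Even the last case removes only 1 − 0.039/0.063 = 38% and 1 − 0.081/0.126 = 36% of the bias. With NMES-only losses of 10% to 20% it removes 1 − 0.028/0.049 = 43% and 1 − 0.119/0.200 = 41%. A gap that opens after discharge is hardly reduced.

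**Scale.** With 18 per arm, the difference detectable with 80% power (two-sided 5%, t-test) is 0.96 SD, and the standard error of the difference is √(2/18) = 0.33 SD. The 75/25 bias is therefore about 0.2 to 0.4 standard errors.

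**The case against.** The attrition sentence is a recruitment allowance, not an analysis rule, and no document says that non-compliers go untested or are dropped. Withdrawal is discretionary and applies to both arms. The SAP compares the randomised groups in a mixed model and names no per-protocol set. Without a compliance threshold, no exclusion could be applied consistently. The trial is exploratory and deliberately uses a demanding stimulus, so the effect when the device is actually used is a legitimate interest. Every input to the bias figures is assumed, and the sign is unknown.

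Much of this stands. Exclusion is not stated, the direction is open, the size is modest, and the effect of actual use is a fair question. It does not remove the point. Comparing randomised groups does not recover 4-week values that were never measured, and two teams following these rules exactly could end with different analysed sets. The phrase placing the final test after the intervention is finished is either only about timing, and so silent on non-compliers, or it ties testing to completion, which makes matters worse. The effect under actual use can be reported as a supportive analysis.

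**Conclusion.** The concern holds. The stated attrition line and withdrawal rule together allow randomised participants to be lost for non-compliance, and nothing requires that they be tested or analysed as assigned. Under the assumptions above, a 75/25 split gives about 0.06 to 0.13 SD of bias, up to 0.24 SD if all 4.8 losses fall in NMES and none if the split is even. The sign depends on whether non-compliers do worse or better. This is small to moderate against a detectable difference of 0.96 SD. It is worth correcting because a 4-week test that was not done cannot be recovered later. Confidence is medium, since neither the split nor the gap is given in the documents.

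**What to change.** - State in the SAP that every randomised participant is invited to the 4-week test and analysed in the assigned group, whatever NMES use was achieved.
- In Withdrawal Procedures, separate stopping use of the device from leaving study assessments, and remove non-compliance as a reason for withdrawal from assessments. Safety withdrawals are unchanged.
- Report losses and reasons by arm, with device-logged use. Make any complier analysis supportive, with its threshold set in advance.
- Restate attrition as loss to the 4-week assessment only: 48 × 0.85 = 40.8, about 20 per arm. This is before post-operative exclusions, and it is an upper limit if some non-compliers decline the test. Enrolment stays at 48.

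The cost is wording plus at most about 5 extra 4-week tests (4.8 of 48) on people already enrolled. The drawback is dilution. With 20.4 per arm the detectable difference is 0.90 SD. If non-compliers gain nothing, the detectable effect in compliers becomes:

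- Even split: 0.90 / (1 − 2.4/20.4) = 1.02 SD, against 0.96 SD for compliers only (18 v 18).
- 75/25 split: 0.90 / (1 − 3.6/20.4) = 1.09 SD, against 0.96 SD (16.8 v 19.2).
- All in NMES: 0.90 / (1 − 4.8/20.4) = 1.18 SD, against 0.97 SD (15.6 v 20.4).
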